#### 10.4.1.1. *Model evaluation*

Assessment of model adequacy and decisions about increasing model complexity will be driven by the data and guided by goodness-of-fit criteria, including:

1. visual inspection of diagnostic scatter plots (observed vs. predicted concentration, residual/weighted residual vs. predicted concentration or time and histograms of individual random effects, for example),
2. successful convergence of the minimization routine with at least 2 significant digits in parameter estimates,
3. plausibility of parameter estimates,
4. precision of parameter estimates,
5. correlation between model parameter estimation errors <0.95, and
6. the Bayesian information criterion (BIC), given the minimum objective function value and number of estimated parameters.

For the nonlinear fixed effects models, additional diagnostic plots will be produced:

7. objective function values across multiple fits from randomised initial guesses, and
8. profile likelihood plots

All parameter estimates will be reported with a measure of estimation uncertainty, such as the relative standard error of the estimates. The individual PK fits will be used to evaluate the adequacy to use the individual PK parameter estimates as regression parameters for PD modeling.

The adequacy of simulation with the selected models will be evaluated by visual predictive checks (VPCs). VPCs for each dose level will be performed by simulation of the study 200 times taking parameter estimation uncertainty into account. 95%-confidence intervals for the 5th percentile, the median, and the 95th percentile will be derived and compared to the corresponding values based on the data.

#### 10.4.2. *Building a PK model*

The PK of MMV367 will be modeled using compartmental models describing the absorption after oral administration, distribution between central and peripheral compartments, and the elimination from the central compartment. The visual data analysis will guide the selection of models that will be tested (e.g., with respect to number of compartments, linear or saturable elimination, absorption kinetics and error model). Covariates will be included if appropriate. Estimations will be done using SAEM algorithm in Monolix. Other appropriate methods may be used if advisable.

FIH data from MMV\_MMV367\_21\_01\_FIH has previously indicated that MMV367 PK is adequately described by a one-compartment model with first order absorption parameterized in terms of  $CL/F$ ,  $Vc/F$  and  $ka$ . Therefore, this structural model will initially be used to model MMV367 PK using the PK modeling dataset. If required to adequately describe MMV367 PK, structural models with greater numbers of compartments and different absorption models (eg first-order rate, lag, transit compartments) will be fitted.

An exploratory investigation of covariate-parameter relationships will be undertaken during the PK modelling step. The covariate WT0 on the clearance and volume parameters will be included to allow predictions in children. Since the body weight distribution may be narrow, the exponents will be fixed to 0.75 and 1 respectively on clearances and volumes of distribution. Other covariates of interest may include AGE, SEX, Infection status and PLbase – however, depending on the population make-up of these covariates, some may not be included. In the event that the distributions of WT0 and AGE are very narrow, a reference value for the population may be used instead of individual participant covariates.

Covariate modeling will be undertaken in the following steps:

- Pre-defined covariate-parameter relationships will be identified based on exploratory analysis and mechanistic plausibility – in particular, WT0 on clearance and volume PK parameters (central and peripheral compartments, if appropriate).
- A full model will be constructed, avoiding simultaneous inclusion of covariates with correlation coefficients  $>0.5$ .
- Population parameters will be estimated (both fixed effects [covariate coefficients and structural model parameters] and random effects).
- An exploratory assessment of any remaining trends will be conducted by graphical inspection of all covariate effects (plots of MAP Bayes estimates of individual random effects and/or WRES from the full model vs. covariates).
- Inferences about clinical relevance of parameters will be based on the resulting parameter estimates of the full model and measures of estimation precision (asymptotic standard errors, bootstrap 95% confidence intervals or log-likelihood profile).
- No hypothesis testing will be conducted.
- This approach enables the direct assessment of clinical relevance of covariate effects and also provides some explanation for the apparent absence of a covariate effect (true lack of an effect vs. lack of information about that effect).

Based on diagnostics plot (if shrinkage is less than  $>30\%$ ) the estimation of random effect covariance matrix will be considered. Additionally, it will be attempted to estimate the full random effect covariance matrix. In order to assess the identifiability of the correlations between random effects, parameter estimations will be repeated from randomly chosen initial guesses for the fixed effect parameters that are estimated. All resulting parameters, including the correlation estimates for the random effects will be compared.

#### 10.4.3. *Building a PD model*

PD model development will be done using gradient based algorithms in IQRTools SysFit. The selected model will then be estimated with SAEM in Monolix to attempt to estimate IIV. Other appropriate methods may be used if advisable. As a general concept the changes in living parasite  $P$  are modeled as the effect of a net exponential growth rate  $GR$  and a killing or clearance rate  $Kill$  due to MMV367. The initial parasitemia  $P_{base}$  at time  $t_0$  will be derived from the mean parasitemia which was observed at treatment administration and a parameter  $PLerr$  to allow for population and individual deviations. The equations are expressed in the log-scale such as:

$$\begin{aligned}\frac{dPL}{dt} &= GR - Kill \\ PL(t_0) &= PL_{base} + PLerr\end{aligned}$$

where  $PL = \ln(P)$  is the log-transformed parasite counts.

Different models describing the relationship of MMV367 plasma concentration on the killing rate may be tested.

#### 10.5. *PK/PD Endpoints*

- PK/PD equations comprising the final structural model
- Primary PK and PD parameters that make up the final structural model: estimated typical values with 90% confidence interval

## 10.6. Presentation of Results

A statistical and graphical analysis of the data (based on the general analysis dataset) will be included.

The analysis results will be reported in the main body of the CSR and technical details will be reported as an appendix (referred to here as the 'technical appendix'). The technical appendix will include the clinical data used in the analysis, data assembly, modelling methods, all results, discussions, and conclusions.

Key results will include description and interpretation of the selected model, parameter estimates, diagnostic plots of goodness-of-fit and will be included in the main text. Limitations of the model prediction will be discussed in the Discussion section of the technical appendix and mentioned in the main text of the CSR.

## 11. SECONDARY ENDPOINTS ANALYSIS

### 11.1 PD Analysis

#### Analysis Set: PD Analysis Set

PD endpoint: The parasite clearance kinetics following dosing with MMV367.

#### 11.1.1 Data Handling

##### Handling of replicates

The data will be recorded as triplicate parasitaemia values for each participant at each time point. The replicate data will be summarised by calculating the geometric mean of the parasitaemia values per participant and time point and will be log10 transformed for statistical analyses.

##### Handling of missing data

Missing parasitaemia data will not be imputed. For any replicates that were non-detects (ND), the value will be substituted with 1 parasite/mL prior to calculating the geometric mean for parasitemia quantified from qPCR.

#### 11.1.2 Parasite clearance kinetics

The Parasite Reduction Ratio (PRR) and corresponding parasite clearance half-life ( $PCt_{1/2}$ ) of asexual parasites is derived from the clearance rate of parasitaemia after administration of MMV367 treatment. The analysis of PD response to investigational antimalarial therapy consists of:

- calculating the optimal parasite clearance rate (slope coefficient from the log-linear decay regression of qPCR data) for each individual, then,
- estimating dose specific parasite clearance rate and 95% confidence interval (CI) by calculating the weighted average slope estimate and corresponding standard error (SE) using an inverse-variance method.

The data used for all model selection and fitting calculations is comprised of the  $\log_{10}$  transformed geometric mean of parasitaemia per time point per participant up to the first time point all parasitaemia replicates are ND. If during initial parasite clearance there are no samples ND for a participant, the last time point included in the analyses will be three time points after the minimum observed parasitemia value. All subsequent time points are set to 'missing' regardless of whether parasitaemia values increased afterwards due to potential

recrudescence. Sensitivity analyses may be performed using other thresholds to determine parasite clearance, for example, but not limited to, the lower limit of quantification (LOQ) (i.e. the lower limit of the reportable range) of 32 parasites/mL or limit of detection of 111 parasites/mL [1], to assess robustness of PRR estimates.

The PRR per 48 hours,  $PRR_{48}$ , for asexual parasite will be estimated using the slope of the optimal fit of the log-linear relationship of the parasitaemia decay over time from MMV367 administration for each individual, as detailed in CTM QIMR SOP 41 and Marquart et al. [2]

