4 STUDY DESIGN

4.1 OVERALL DESIGN

This is an open-label, adaptive study that will utilise the *P. falciparum* induced blood stage malaria (IBSM) model to characterise the pharmacokinetic/pharmacodynamic (PK/PD) profile and safety of MMV367 (the IMP). Up to 18 participants will be enrolled in cohorts of up to 6 participants each. The study will proceed as follows for all participants:

- Screening period of up to 28 days to recruit healthy adult volunteers.
- Day 0: Intravenous inoculation with approximately 2,800 viable *P. falciparum*-infected erythrocytes.
- Days 1-3: Daily follow up via phone call or text message.
- Days 4-7: Daily site visits for clinical evaluation and blood sampling to monitor malaria parasitaemia via quantitative polymerase chain reaction (qPCR).
- Day 7 PM: Start of confinement within the clinical trial unit.
- Day 8: Administration of a single oral dose of the IMP (MMV367). Different doses of MMV367 will be administered across and within cohorts in order to effectively characterise the PK/PD relationship (see Section 4.3 for dose selection rationale).
- Days 8-11: Regular clinical evaluation and blood sampling to monitor malaria parasitaemia and measure MMV367 plasma concentration.
- Day 11 AM: End of confinement within clinical trial unit.
- Days 12-23: Outpatient follow-up for clinical evaluation and blood sampling.
- Day 24: Initiation of compulsory definitive antimalarial treatment with Riamet® (artemether/lumefantrine) and/or other registered antimalarials if required (see section 6.1). Treatment will be initiated earlier than Day 24 in the event of:
 - Insufficient parasite clearance following IMP dosing (parasitaemia not reduced ≥ 10 -fold by Day 10 compared with peak parasitaemia on Day 8).
 - Parasite regrowth following IMP dosing (initial parasite clearance is followed by asexual parasite regrowth above 5000 parasites/mL).
 - Participant discontinuation/withdrawal (see Section 7),
 - Investigator's discretion in the interest of participant safety.
- Day 27: End of study visit for final clinical evaluation and to ensure complete clearance of malaria parasitaemia (at least one negative malaria PCR result required).

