The PRR_{48} will be estimated using the slope of the optimal fit of the log-linear relationship of the parasitaemia decay. The optimal fit will be derived using summarised replicate parasitaemia data, which have been cleaned by dealing with potential outliers, values below the limit of detection and non-detectable values. The optimal fit of the log-linear parasitaemia-by-time relationship is determined by using left and right censoring to systematically remove the potential lag phase and tail phase of the parasitaemia decay. The decay rate, estimated by the slope coefficient from the log-linear decay regression, will be calculated for each participant. The overall dose-specific PRR_{48} will be estimated with its 95% CI by calculating the weighted average slope estimate and corresponding standard error (SE) using an inverse-variance method. Only participants who have optimal regression models with appropriate fit contribute toward the dose-specific PRR_{48} . Details will be presented in the SAP.

The parasite clearance half-life ($PCt_{1/2}$) will be derived from the optimal decay rate. $PCt_{1/2}$ is a transformation of PRR_{48} into a per hour clearance rate. Details regarding the calculation of this parameter will be presented in the SAP.

PK parameters:

The following PK parameters will be determined using non-compartmental methods from plasma MMV367 concentration-time profiles: AUC_{last} , AUC_{inf} , C_{max} , t_{max} , $t_{1/2}$, CL/F , Vd/F and λ . When applicable, all PK variables (normally and log-normally distributed) will be summarized using arithmetic and geometric means, minimum, median, maximum, standard deviation (SD) and coefficient of variation (CV %) of arithmetic and geometric means. Summary tables showing the median and range for t_{max} and geometric mean and CV% for all other PK variables will be provided by dose.

Plasma concentration values below the lower limit of quantification will be set to zero. All mentioned parameters will be expressed as mean \pm SD, unless otherwise stated. Details regarding the calculation of this parameter will be presented in the SAP.

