#### **5.1.4 *PD Analysis Set***

The PD analysis set will include all participants inoculated with the malaria challenge agent and who develop parasitaemia detectable by qPCR, received a dose of MMV367, and have no protocol deviations that would exclude them from the PD analysis due to their impact on the PD analysis.

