### 10.3 Data Assembly

#### 10.3.1 Master PK/PD dataset

Data from study MMV\_MMV367\_22\_01\_VIS will contain information on the individual MMV367 doses, MMV367 PK concentrations, the triplicated parasitemia levels, gametocyte data and typical covariates such as age, height, weight, sex and race. Data from study MMV\_MMV367\_21\_01\_FiH will be added to increase the number of individuals with PK profiles.

A master dataset will be assembled formatted according to the MMV dataset standard. (cf., "MS\_IQdataset\_V4"). Plasma concentration will be in ug/mL, total parasite levels in counts/mL, and doses in mg. Gametocyte data is in copies/uL.

Parasite data after the first administration of rescue medication is flagged by setting the IGNORE column to "Rescued". The time in hours is relative to the (first) MMV367 administration time. Gametocyte data will be converted to parasite counts following the

instructions in "Analyzing RNA data by [name] Nov2017.docx". Total counts of parasites were flagged to be ignored (by setting the column IGNORE to "gametocytes") if counts of gametocytes exceeded 10% of total counts.

A general analysis dataset will then be created from the master dataset. The general dataset will contain the following observations: MMV367 plasma concentrations, total parasite count, as well as counts of gametocytes. In addition, dosing records for *P. falciparum* inoculation, MMV367 administration and rescue medication administration will be defined.

The following covariates will be included as additional columns in the general dataset.

- DOSELEVEL: the dose amount
- DOSEMULT: the number of doses
- WT0: body weight (kg)
- AGE: age (years)
- SEX: sex (male or female)
- Infection status (for all participants from MMV\_MMV367\_22\_01\_VIS infection status will be positive; For all participants from MMV\_MMV367\_21\_01\_FIH infection status will be negative.)
- PLbase: The model baseline parasitemia value – the geometric mean of parasite counts at time of first MMV367 dose.

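### SAP 11.1.1–11.1.2 does not end the PRR48 series at the first dose of definitive treatment, so Riamet clearance can enter the slope of a participant treated early for insufficient response

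*SAP*

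**What the plan says.** - **End of series (SAP 11.1.2).** The regression data are the log10 "transformed geometric mean of parasitaemia per time point per participant up to the first time point all parasitaemia replicates are ND". If no such point occurs during initial clearance, "the last time point included in the analyses will be three time points after the minimum observed parasitemia value". The method is "as detailed in CTM QIMR SOP 41" and in a cited methods paper.
- **Non-detects (SAP 11.1.1).** For a non-detect (ND) replicate, "the value will be substituted with 1 parasite/mL prior to calculating the geometric mean".
- **Cleaning (Protocol 9.4.3).** The data are to be "cleaned by dealing with potential outliers, values below the limit of detection and non-detectable values". Samples taken after definitive treatment are not on that list.
- **Early treatment (Protocol 4.1).** One trigger for definitive treatment before Day 24 is "Insufficient parasite clearance following IMP dosing", meaning a fall of less than 10-fold by Day 10 from the Day 8 peak.
- **Sampling after treatment (Protocol 8.1.2).** PCR continues until at least one negative result.
- **Analysis set (SAP 5.1.4).** PD set members must "have no protocol deviations that would exclude them from the PD analysis due to their impact on the PD analysis". Early treatment given under the protocol is not a deviation, so these participants stay in.
- **PK/PD dataset (SAP 10.3.1, 10.3.3).** "Parasite data after the first administration of rescue medication is flagged by setting the IGNORE column" to a rescued value, and flagged records are removed before modelling. Section 11.1 has no equivalent, and SAP 4.1.2.3 places the final PD parameters in a separate PRR report.

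**The concern.** Two analyses of the same qPCR data follow different written rules. The primary model drops post-rescue samples; the PRR48 regression, read literally, keeps them. A participant treated because MMV367 did not clear parasites well enough will normally first become ND under Riamet, and that is where the SAP ends the series.

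The window search in Table 2 of SAP 11.1.2 gives no protection. It trims one end at a time and keeps the window with the smallest p-value. A steep Riamet decline lowers the p-value, so the search favours windows that contain it.

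What is at stake is the individual PRR48 and PCt1/2 of such a participant, and through inverse-variance weighting the dose mean and the between-dose test in SAP 11.1.2. Someone treated because the fall was below 10-fold can be reported with a fall above 10-fold and a narrow interval.

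**Working it through.** The documents give no figure on this point, so there is none to reproduce. The check applies the written algorithm to simulated profiles.

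**From the documents.** PCR at 0, 2, 4, 8, 12, 16, 24, 30, 36, 48, 54, 60 and 72 h, then the outpatient times to 216 h. ND set to 1 parasite/mL. Table 2 search down to four points, fit accepted if p<0.001. PRR48 = 10^(−48β); PCt1/2 = 48 × log10(2) / log10 PRR48.

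**Assumed.** Start 20,000/mL, no lag, residual SD 0.2 log10, ND below 10/mL, Riamet clearing 3 log10 per 48 h without delay. True log10 PRR48 is 0.5. Only profiles with an observed fall below 10-fold at 48 h are kept, because these meet the trigger. The SAP does not say whether the first ND point itself belongs to the series, so both readings were run.

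| Treated at | First ND point | Median log10 PRR48 | Profiles reported at 1.0 or more |
|---|---|---|---|
| 50 h | included | 1.62 | about 90% |
| 50 h | excluded | 1.10 | about 67% |
| 73 h | included | – | about 89% |
| 73 h | excluded | 0.83 | about 6% |
| 50 h, series cut at treatment | – | – | about 3% |

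In the 50 h rows the 95% CI excludes the true value in 97–99% of accepted fits. On the reporting scales:

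- Truth 0.5: 10^0.5 = 3.2-fold; half-life 14.45/0.5 = 28.9 h.
- Reported 1.62: 42-fold; 14.45/1.62 = 8.9 h.
- Reported 1.10: 12.6-fold; 14.45/1.10 = 13.1 h.
- Reported 0.83: 6.8-fold; 14.45/0.83 = 17.4 h.

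**Sensitivity.** With treatment at 49, 55 or 61 h and an ND limit of 3, 10 or 32/mL, 58–100% of profiles (ND included) or 16–96% (ND excluded) reach 1.0. A separate coding (Riamet 2–4 log10 per 48 h, SD 0.1–0.3, treated at 48–60 h, ND included) gave medians of 1.27–1.75 for a true 0.5, with upward bias in every scenario.

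**How often.** Protocol 4.3 predicts log10 PRR48 at 20 mg with median 2.9 and interval 0.26 to 5.8. Reading this as a normal interval for individuals (an assumption):

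- SD = (5.8 − 0.26)/3.92 = 1.41
- P(below 1.0) = Φ((1 − 2.9)/1.41) = 0.089
- At least one of three = 1 − 0.911³ = 0.24

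The same reading at 90 mg (3.6; 1.8 to 6.2) gives about 1% per participant.

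**What the cut does to a dose mean.** Cut at 50 h, only 10–11% of the true-0.5 series pass p<0.001, so most such participants drop out. For a group with one participant at 0.5 and two at 2.9 (simple mean (0.5 + 2.9 + 2.9)/3 = 2.1), the dose mean is 1.68–2.86 as written and 1.77–3.35 after the cut, over the settings tried. The cut corrects the individual value but can raise the mean of a mixed group.

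**The case against.** **The rule may exist elsewhere.** SAP 11.1.2 defers to SOP 41 and a methods paper, neither of which is available here. This stands: the documents show that the SAP is silent, not that post-Riamet samples will be analysed. But the SAP writes out the end-of-series rule and the algorithm in full without a cut, so a reader following it would not apply one.

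**Initial clearance may mean clearance before rescue.** This is a fair reading, and SAP 11.1.2 does describe PRR as clearance after MMV367. It reduces the problem without closing it. If the pre-treatment minimum is at 48 h, the next three time points are 54, 60 and 72 h, all after a 50 h treatment. On this reading 24–29% of profiles still reach 1.0 when treated at 50 h, and 65–72% at 61 h.

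**Treatment at 50 h is early.** This stands as to size. PCR turnaround is not stated, and Day 10 samples run from 48 to 60 h. At 73 h with the ND point excluded, few profiles reach 1.0, although the median is still above the truth.

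**Safeguards exist.** The primary model also derives log10 PRR48 (Protocol 9.4.2) from data without post-rescue records, rescue dates are listed (SAP 7.1), and individual fits are plotted (SAP 11.1.3). These help a careful reader but do not correct the tabulated endpoint.

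**Stronger readings a reader might infer.** One is that a failing dose would look active. That needs most of a dose group to fail; on the figures above, all three failing at 20 mg has probability 0.089³ = 0.07%. Another is that early treatment for COVID-19 distorts PRR48 in the same way. That needs a positive result soon after dosing despite negative tests on Day 6 and Day 7, and it disappears if the ND point is excluded. The documents support neither as a material concern.

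**Conclusion.** The gap is real and should be closed. As written, SAP 11.1.1–11.1.2 lets post-Riamet samples into the regression of a participant treated for insufficient clearance, and the bias is toward faster clearance. For a true log10 PRR48 of 0.5 the reported median is about 0.8 to 1.6. This range rests on the assumed Riamet rate of 3 log10 per 48 h, treatment between 50 and 73 h, and the handling of the first ND point. Residual SD and starting parasitaemia are also assumed.

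The scope is limited. It is a secondary endpoint, and the issue arises mainly at 20 mg or below (Protocol 4.3 allows a lower dose in Cohort 2). It concerns participants who have not reached ND before treatment. A reader might infer that the primary PK/PD result or the choice of doses is compromised. The documents do not support that: SAP 10.3.1 and 10.3.3 remove post-rescue records from the modelling data, and Protocol 4.3 bases later doses on PK/PD simulations.

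**What to change.** Add to SAP 11.1.1, consistent with 10.3.1:

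> Parasitaemia samples taken after the first dose of definitive antimalarial treatment are set to missing before the end-of-series rule and the Table 2 algorithm are applied.

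If SOP 41 already has this rule, state it in the SAP. It would also help to say whether the first ND point is part of the series.

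Because the cut will often make early-treated participants fail the p<0.001 screen, give for each dose the number treated early and the number contributing to the mean, and list the pre-treatment slope and CI of those not contributing. A sensitivity dose mean that includes those slopes is optional.

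The cost is one sentence, one footnote and one short listing, with no extra participants or samples. The drawback is that the mean of a mixed dose group may rise when the poor responder drops out, which the footnote and listing make visible.

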#### **4.1.2.3 PD Laboratory**

All parasitaemia data will be generated by the Queensland Paediatric Infectious Diseases (QPID) laboratory and captured electronically using MARS (18S qPCR parasitaemia data). All parasite life-stage data (i.e. gametocytæmia and ring-stage parasites) will be generated by the QPID laboratory and transferred electronically to the Queensland Institute of Medical Research (QIMR) Berghofer and this data will be used for PK/PD modelling. QIMR will provide the 'raw' PCR data 18S, the female gametocyte-specific transcript (pfs25), the male gametocyte-specific transcript (pfMGET) and the ring-stage transcript (pfSBP-1) to SSR as per DTS, and final PD parameters will be in the PRR report.

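### The PRR48 data window in SAP 11.1.2 is not closed at definitive antimalarial treatment, so participants treated before any all-ND sample get a PRR48 that includes post-Riamet decline

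*SAP*

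**What the plan says.** SAP 11.1.2 defines the data for every PRR48 fit. The main rule takes samples "up to the first time point all parasitaemia replicates are ND". The fallback begins "If during initial parasite clearance there are no samples ND for a participant", and then "the last time point included in the analyses will be three time points after the minimum observed parasitemia value". Later points are discarded: "All subsequent time points are set to 'missing' regardless of whether parasitaemia values increased afterwards due to potential" recrudescence. The optional sensitivity analyses vary only the threshold for clearance. Further detail is deferred: "as detailed in CTM QIMR SOP 41" and in a cited methods paper.

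For the primary analysis, SAP 10.3.1 does deal with treatment: "Parasite data after the first administration of rescue medication is flagged by setting the IGNORE column to" a rescued status. SAP 10.3.3 then removes flagged records. PRR48 is produced by a separate route, since "final PD parameters will be in the PRR report" (SAP 4.1.2.3).

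Protocol 4.1 starts Riamet before Day 24 for, among other reasons, "Insufficient parasite clearance following IMP dosing", meaning less than a 10-fold fall by Day 10 from the Day 8 peak. Other triggers are regrowth above 5000 parasites/mL, withdrawal and investigator discretion. Protocol 8.2.7.11 adds a positive COVID-19 test after dosing. Under Protocol 8.1.2, PCR sampling after treatment goes on until at least one negative result.

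**The concern.** PRR48 and PCt1/2 are meant to describe clearance by MMV367. If a participant is treated before any sample is all-ND, the first all-ND sample arises under Riamet, and the window in 11.1.2 runs through the treated period to reach it. Nothing else in the SAP removes these data. The PD analysis set (SAP 5.1.4) excludes only on protocol deviations, and protocol-mandated treatment is not one. Protocol 9.4.3 mentions outliers, values below the detection limit and lag and tail phases, but not rescue.

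The groups are small: 3, 2 and 1 in Cohort 1, and Cohort 2 may use a dose below 20 mg. One affected slope can be a third or more of a dose group. It enters both the dose-specific PRR48 and the between-dose test in 11.1.2.

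**Working it through.** The plan states no PRR48 result or power figure to reproduce, so the check runs the SAP's own rules on the protocol's sampling times.

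**Inputs from the documents.** PCR at 0, 2, 4, 8, 12, 16, 24, 30, 36, 48, 54, 60, 72, 96, 120, 168 and 216 h and later. ND entered as 1 parasite/mL. SAP Table 2 trimming: drop the first or last point, keep the lower p-value, stop at four points, choose the smallest p-value. A fit counts if p<0.001. log10 PRR48 = −48 × slope. Day 10 is 48 h after the Day 8 dose.

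**Assumptions not in the documents (range tried).** Baseline 10^4/mL; log10 noise SD 0.25 (0.15–0.4); ND below 10/mL (2–111); Riamet log10 PRR48 of 3 (2–4); rescue just after the 48 h sample (also 72 h).

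**Step 1, without noise.** Take a true MMV367 log10 PRR48 of 0.5.
- At 48 h the level is 4 − 0.5 = 3.5.
- Riamet then removes 3/48 = 0.0625 log10 per hour, so the ND limit (1.0 on the log10 scale) is reached (3.5 − 1.0)/0.0625 = 40 h later, at 88 h.
- The first all-ND sample is at 96 h. The window includes 54, 60, 72 and 96 h, all after Riamet.

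Reading the initial-clearance condition as pre-rescue does not close the gap. If the pre-rescue minimum is at 48 h, three further samples are 54, 60 and 72 h. If it is at 36 h, they are 48, 54 and 60 h.

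**Step 2, with noise (400–1000 simulated participants per scenario, true 0.5).** Half-life by SAP Equation 8 is log10(2) × 48 / log10 PRR48 = 14.45 / log10 PRR48, so the true value is 14.45/0.5 = 28.9 h.

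| Window | Median log10 PRR48 | Half-life at that median | Pass p<0.001 | Fit extends past rescue |
|---|---|---|---|---|
| Literal | 1.64 | 8.8 h | 100% | 100% |
| Initial clearance read as pre-rescue | 1.01 | 14.3 h | 47% | 71% |
| Cut at rescue | 0.80 | 18.1 h | 7% | 0% |

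The cut estimate is itself above 0.5. It contains no post-rescue data, so that excess is not a rescue effect.

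For true values of 0 to 0.9 the literal window gives 1.63–1.75 with 90–100% passing. Cut at rescue, it gives 0.27–1.01 with 0.5–26% passing. Over the assumption ranges at true 0.5, the literal window gives 0.92–1.77 and the cut window 0.59–1.09, and the direction did not change. The pre-rescue reading is less uniform: with a 12 h lag it gave 0.70 against 0.76 for the cut, though 26% against 7% passed.

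**Step 3, regrowth.** Decay of 2.9 per 48 h, lowest point at 48 h, back to baseline and rescued at 168 h (the 7-day median in Protocol 4.3). With the initial-clearance condition applied, the estimate is 2.64–2.80, the same as with a cut, and no fit extends past rescue.

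**Step 4, frequency.** Assume that the 20 mg prediction in Protocol 4.3 (2.9, 0.26 to 5.8) is a normal between-person spread.
- SD = (5.8 − 0.26)/3.92 = 1.41; z = (1 − 2.9)/1.41 = −1.34; P(log10 PRR48 < 1) is about 9% per participant.
- At least one of three: 1 − 0.91³, about 24–25%.
- At 90 mg (3.6, 1.8 to 6.2) the same sum gives about 1% per participant.

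**Step 5, dose level.** Three participants, one failure at 0.5 and two at 2.9: true mean (0.5 + 2.9 + 2.9)/3 = 2.1. The dose-specific median is 2.62 on the literal window and about 3.16 after the cut. With two failures the true mean is (0.5 + 0.5 + 2.9)/3 = 1.3, and the results are 2.14 literal and 3.15 cut. The cut takes about 93% of such failures out through the p<0.001 criterion.

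**The case against.** Four points can be made for the plan.

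- A reader might infer that Riamet clearance is credited to MMV367 in every participant in whom MMV367 fails. The documents do not support that. The failure expected at 20 mg is clearance followed by regrowth, and the initial-clearance condition with the set-to-missing rule closes the window before rescue in those participants (Step 3). Even if the first all-ND sample is taken from anywhere in the profile, the main error there is a wrongly selected regrowth limb (median about −1.0 to −1.2), not Riamet decline. This objection stands and limits the point to treatment before ND without regrowth.
- A reader might also infer that trimming discards the MMV367 phase as lag and fits pure Riamet decline. It does not. At true 0.5 the chosen fit starts at a median of 0 h, and only 4% start at or after 36 h. The slope is a blend of the two phases.
- Cutting at rescue alone makes the dose-specific PRR48 worse in mixed groups (Step 5). This stands, and the fix has to deal with it.
- The SOP named in 11.1.2 may contain a cut at rescue. It may, but it is not in the documents. The SAP states its own window explicitly, and an unseen SOP cannot be assumed to override it.

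The endpoint is also secondary and largely descriptive, and cohort doses are chosen from PK/PD simulations.

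**Conclusion.** The point holds in a limited form. Followed as written, SAP 11.1.2 lets post-Riamet decline into the individual slope of participants treated before any all-ND sample. These are mainly participants with less than a 10-fold fall by Day 10; early treatment for COVID-19, withdrawal or investigator discretion is exposed in the same way. PRR48 is inflated and PCt1/2 shortened for those participants: a true 0.5 becomes about 1.6 on the literal window and about 1.0 on the pre-rescue reading, against about 0.8 when cut. The size depends on the assumed Riamet rate, noise and ND limit. The direction for the literal window did not change over the ranges tried.

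Few participants are likely to be affected at 20 mg (about 9% each, on an assumed reading of the protocol's interval) and fewer at 90 mg. Failure would be likelier at a dose below 20 mg. The primary PK/PD endpoint is not affected. The SAP should be corrected before database lock, because a stated rule gives a wrong individual result and the primary dataset already applies the right exclusion.

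**What to change.** In SAP 11.1.2:

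1. Set parasitaemia after the first dose of any definitive antimalarial to missing, as 10.3.1 does for the PK/PD dataset.
2. Define the first all-ND sample, initial parasite clearance and the minimum observed value on pre-rescue data only.
3. Define Time in Equation 1 as hours since MMV367 administration. The present definition refers only to antimalarial treatment.
4. As a necessary companion, report by dose the number treated before ND and the number of these excluded by the p<0.001 criterion, and list their pre-rescue slopes. Give a sensitivity dose-specific PRR48 that includes those slopes regardless of that criterion.

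The cost is a few lines of SAP text, one listing and one extra estimate per dose. Rescue dosing records are already planned in 10.3.1, so no new data are needed. The drawback is that some rescued participants will have few points and imprecise slopes. Without item 4 most of them would leave the dose-specific PRR48, which would bias it upward.
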